If a clinically significant laboratory abnormality is a sign of a disease or syndrome (e.g., ALP and bilirubin $5 \times$ upper limit of normal (ULN) associated with cholestasis), only the diagnosis (i.e., cholestasis) should be recorded on the Adverse Event eCRF.

If a clinically significant laboratory abnormality is not a sign of a disease or syndrome, the abnormality itself should be recorded on the Adverse Event eCRF, along with a descriptor indicating whether the test result is above or below the normal range (e.g., "elevated potassium," as opposed to "abnormal potassium"). If the laboratory abnormality can be characterized by a precise clinical term per standard definitions, the clinical term should be recorded as the adverse event. For example, an elevated serum potassium level of 7.0 mEq/L should be recorded as "hyperkalemia."

Observations of the same clinically significant laboratory abnormality from visit to visit should only be recorded once on the Adverse Event eCRF (see Section A2-7.3 for details on recording persistent adverse events).

A2-7.5 Abnormal Vital Sign Values

Not every abnormal vital sign value qualifies as an adverse event. A vital sign abnormality that is associated with the underlying disease should not be reported as an adverse event unless judged by the investigator to be more severe than expected. A vital sign abnormality that is not associated with the underlying disease must be reported as an adverse event if it meets any of the following criteria:

- Is accompanied by clinical symptoms
- Results in a change in study treatment (e.g., dose modification, treatment interruption, or treatment discontinuation)
- Results in a medical intervention or a change in concomitant therapy
- Is clinically significant in the investigator's judgment

It is the investigator's responsibility to review all vital sign findings. Medical and scientific judgment should be exercised in deciding whether an isolated vital sign abnormality should be classified as an adverse event.

If a clinically significant vital sign abnormality is a sign of a disease or syndrome (e.g., high blood pressure), only the diagnosis (e.g., hypertension) should be recorded on the Adverse Event eCRF.

Observations of the same clinically significant vital sign abnormality from visit to visit should only be recorded once on the Adverse Event eCRF (see Section A2-7.3 for details on recording persistent adverse events).

A2-7.6 Abnormal Liver Function Tests

The finding of an elevated ALT or AST ($>3 \times ULN$) in combination with either an elevated total bilirubin ($>2 \times ULN$) or clinical jaundice in the absence of cholestasis or other causes of hyperbilirubinemia is considered to be an indicator of severe liver injury (as defined by Hy's Law). Therefore, investigators must report as an adverse event the occurrence of either of the following:

- Treatment-emergent ALT or AST $> 3 \times ULN$ in combination with total bilirubin $> 2 \times ULN$
- Treatment-emergent ALT or AST > 3 × ULN in combination with clinical jaundice

The most appropriate diagnosis or (if a diagnosis cannot be established) the abnormal laboratory values should be recorded on the Adverse Event eCRF (see Section A2-7.4)

6-mg Faricimab Prefilled Syringe—F. Hoffmann-La Roche Ltd 53/Protocol GR43742, Version 1

and reported to the Sponsor immediately (i.e., no more than 24 hours after the investigator becomes aware of the event), either as a serious adverse event or an adverse event of special interest (see Section A2-5).

A2-7.7 Deaths

All deaths that occur during the protocol-specified adverse event reporting period (see Section 8.3.1), regardless of relationship to study treatment, must be recorded on the Adverse Event eCRF and immediately reported to the Sponsor (see Section A2-5).

Death should be considered an outcome and not a distinct event. The event or condition that caused or contributed to the fatal outcome should be recorded as the single medical concept on the Adverse Event eCRF. Generally, only one such event should be reported. If the cause of death is unknown and cannot be ascertained at the time of reporting, **"unexplained death"** should be recorded on the Adverse Event eCRF. If the cause of death later becomes available (e.g., after autopsy), "unexplained death" should be replaced by the established cause of death. The term **"sudden death"** should not be used unless combined with the presumed cause of death (e.g., "sudden cardiac death").

Deaths that occur after the adverse event reporting period should be reported as described in Section A2-6.

A2-7.8 Preexisting Medical Conditions

A preexisting medical condition is one that is present at the screening visit for this study. Such conditions should be recorded on the General Medical History and Baseline Conditions eCRF.

A preexisting medical condition should be recorded as an adverse event only if the frequency, severity, or character of the condition worsens during the study. When recording such events on the Adverse Event eCRF, it is important to convey the concept that the preexisting condition has changed by including applicable descriptors (e.g., "more frequent headaches").

A2-7.9 Unexpected Worsening of nAMD or DME in the Study Eye

Medical occurrences or symptoms of deterioration that are anticipated as part of nAMD or DME should not be recorded as adverse events. However, deterioration that is judged by the investigator to have unexpectedly worsened in severity or frequency or changed in nature at any time during the study should be recorded as an adverse event. When recording an unanticipated worsening of neovascular age-related macular degeneration (nAMD) or diabetic macular edema (DME) on the Adverse Event eCRF, it is important to convey the concept that the condition has changed by including

applicable descriptors (e.g., "accelerated worsening of neovascular age-related macular degeneration"; "accelerated worsening of diabetic macular edema").

A2-7.10 Hospitalization or Prolonged Hospitalization

Any adverse event that results in hospitalization (i.e., inpatient admission to a hospital) or prolonged hospitalization should be documented and reported as a serious adverse event (per the definition of serious adverse event in Section A2-2), except as outlined below.

An event that leads to hospitalization under the following circumstances should not be reported as an adverse event or a serious adverse event:

- Hospitalization for a preexisting condition, provided that all of the following criteria are met:
 - The patient was hospitalized for an elective procedure that was planned prior to the study, was scheduled during the study despite the fact that the condition had not worsened, or was scheduled during the study when treatment became necessary because of the expected normal progression of the condition
 - The patient has not experienced an adverse event

An event that leads to hospitalization under the following circumstances is not considered to be a serious adverse event, but should be reported as an adverse event instead:

• Hospitalization that was necessary because of patient requirement for outpatient care outside of normal outpatient clinic operating hours

A2-7.11 Requirements for Cases of Accidental Overdose or Medication Error

Accidental overdose and medication error (hereafter collectively referred to as "special situations") are defined as follows:

- Accidental overdose: accidental administration of a drug in a quantity that is higher than the assigned dose
- Medication error: accidental deviation in the administration of a drug

In some cases, a medication error may be intercepted prior to administration of the drug.

Note: Special situations are not in themselves adverse events, but may result in adverse events.

Each adverse event associated with a special situation should be recorded separately on the Adverse Event eCRF. If the associated adverse event fulfills seriousness criteria

6-mg Faricimab Prefilled Syringe—F. Hoffmann-La Roche Ltd 55/Protocol GR43742, Version 1

or qualifies as an adverse event of special interest, the event should be reported to the Sponsor immediately (i.e., no more than 24 hours after the investigator becomes aware of the event; see Section A2-5). For 6-mg faricimab PFS, adverse events associated with special situations should be recorded as described below for each situation:

- Accidental overdose: Enter the adverse event term. Check the "Accidental overdose" and "Medication error" boxes.
- Medication error that does not qualify as an overdose: Enter the adverse event term. Check the "Medication error" box.
- Medication error that qualifies as an overdose: Enter the adverse event term. Check the "Accidental overdose" and "Medication error" boxes.
- As an example, an accidental overdose that resulted in a headache would require two entries on the Adverse Event eCRF, one entry to report the accidental overdose and one entry to report the headache. The "Accidental overdose" and "Medication error" boxes would need to be checked for both entries.

All special situations associated with 6-mg faricimab PFS, regardless of whether they result in an adverse event, should be recorded on the Adverse Event eCRF as described below:

- Accidental overdose: Enter the drug name and "accidental overdose" as the event term. Check the "Accidental overdose" and "Medication error" boxes.
- Medication error that does not qualify as an overdose: Enter the name of the drug administered and a description of the error (e.g., wrong dose administered, wrong dosing schedule, incorrect route of administration, wrong drug, expired drug administered) as the event term. Check the "Medication error" box.
- Medication error that qualifies as an overdose: Enter the drug name and "accidental overdose" as the event term. Check the "Accidental overdose" and "Medication error" boxes. Enter a description of the error in the additional case details.
- Intercepted medication error: Enter the drug name and "intercepted medication error" as the event term. Check the "Medication error" box. Enter a description of the error in the additional case details.

Appendix 3 Safety Plan: Management of Identified and Potential Risks

Table of Contents

A3-1 Risks Associated with faricimab......56

A3-1 RISKS ASSOCIATED WITH FARICIMAB

Faricimab is currently approved in the United States, United Kingdom, Japan, Thailand, Switzerland, and the United Arab Emirates for the treatment of nAMD and DME by injection into the eye. Clinical development is ongoing. The safety plan for patients in this study is based on clinical experience with faricimab in completed and ongoing studies. The anticipated important safety risks for faricimab are outlined below. Please refer to the Faricimab Investigator's Brochure for a complete summary of safety information.

Several measures will be taken to ensure the safety of study patients. Following 6-mg faricimab intravitreal (IVT) injection using the PFS configuration, patients will undergo post-treatment observation according to standard clinical practice. Patients will remain at the clinic for approximately 30 minutes after the injection. Intraocular pressure (IOP) will be measured in the study eye at 30 (\pm 15) minutes after treatment. If there are no safety concerns after 30 (\pm 15) minutes following treatment, patients will be allowed to leave the clinic. If any safety concerns or immediate toxicity is noted, the patient will remain at the clinic and will be treated according to the designated physician's clinical judgment. If applicable, the adverse event and treatment of adverse event (if applicable) will be reported on the appropriate electronic Case Report Forms (eCRFs).

All patients will be contacted by study site personnel 3 (± 1) days and 7 (± 1) days after the injection to elicit reports of any adverse events that may have occurred (e.g., decrease in vision, eye pain, unusual redness, or any other new ocular symptoms) in the study eye. Patients will also be asked whether they have taken the prescribed, self -administered, post-injection antimicrobial treatments (if applicable) for their study eye as directed by the investigator.

If warranted during the 7-day safety follow-up period, patients will be asked to return to the clinic as soon as possible for an unscheduled safety assessment visit and will be instructed to contact the investigator at any time should they have any health related concerns. Refer to Appendix 9 for information on assessments required at unscheduled safety visits.

The safety plan for patients in this study consists of monitoring of safety events (including adverse events, serious adverse events, and adverse events of special interest) during the study period. Faricimab drug in the PFS has the same formulation and concentration, and is injected at the same dose, volume, route of administration, and injection procedure as the faricimab supplied in a vial configuration and studied in the Phase III program.

The risks associated with faricimab are published in the Investigator's Brochure. These risks of faricimab include, but are not limited to, intraocular inflammation and increased

6-mg Faricimab Prefilled Syringe—F. Hoffmann-La Roche Ltd 58/Protocol GR43742, Version 1

IOP. Refer to the current version of the Faricimab Investigator's Brochure for more details on the risks of faricimab.

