1.2 STUDY SCHEMA

Figure 1 Study Schema

BCVA=best-corrected visual acuity; FPI=first patient in; HCP=health care provider; ICF=Informed Consent Form; IFU=Instructions for Use.

Note: There will be approximately 2–3 HCP teams, with 35 patients in total. Study start corresponds with Day 1 (FPI). Study end is 7 days after the injection in the last patient. The injection procedure (study Day 1 in the schematic) can occur on different calendar days for different HCPs and different patients. HCPs will review the IFU on their own before Day 1 of the study. HCP interviews will be conducted on Day 1.

*Baseline examinations consist of BCVA, slitlamp, and indirect ophthalmoscopy.

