4.4 END OF STUDY DEFINITION

A patient is considered to have completed the study if he or she has completed all phases of the study, including the safety telephone call 7 days after administration of the PFS injection.

The end of this study is defined as the date when approximately 35 patients have received injections, all HCP participants have completed their interviews with the HF observers, and the 7-day (\pm 1 day) reporting period after the PFS injection in the last patient has passed. It is expected that the duration of the investigation (length of study plus enrollment period) will be approximately 1.5 months.

In addition, the Sponsor may decide to terminate the study at any time.

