8.3 ADVERSE EVENTS, SERIOUS ADVERSE EVENTS, AND OTHER SAFETY REPORTING

The definitions of adverse event and serious adverse event can be found in Appendix 2.

Adverse events will be reported by the patient (or, when appropriate, by a caregiver, surrogate, or the patient's legally authorized representative).

The investigator and any qualified designees are responsible for detecting, documenting, and recording events that meet the definition of an adverse event or serious adverse event and remain responsible for following up adverse events that are serious, are considered related to the study treatment or study procedures, or caused the patient to discontinue the study (see Section 7).

8.3.1 Time Period and Frequency for Collecting Adverse Event and Serious Adverse Event Information

After informed consent has been obtained but prior to initiation of study drug, only serious adverse events caused by a protocol-mandated intervention should be reported (see Appendix 2). All other medical occurrences deemed significant by the investigator that begin before the start of study treatment but after obtaining informed consent will be recorded on the relevant medical history eCRF, not the Adverse Event eCRF.

All adverse events (ocular and non-ocular) will be reported from the start of treatment until Day 7 after the faricimab PFS injection procedure (see Section 1.3).

All serious adverse events will be recorded and reported to the Sponsor or designee immediately and under no circumstance should this exceed 24 hours, as indicated in Appendix 2. The investigator will submit any updated serious adverse event data to the Sponsor within 24 hours of it being available.

The 7-day reporting period has been determined based on the expected timing of potential procedure-related events. In addition, all patients will be instructed to immediately contact their retina specialist if their eye becomes red, sensitive to light, painful, or develops a change in vision any time after the injection, including after the reporting period ends.

Investigators are not obligated to actively seek adverse event or serious adverse event information after conclusion of study participation. However, if the investigator learns of any serious adverse event, including a death, at any time after a patient has been

6-mg Faricimab Prefilled Syringe—F. Hoffmann-La Roche Ltd 27/Protocol GR43742, Version 1

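### Follow-up calls: Appendix 3 limits the adverse events asked about to the study eye, against the all-event scope elsewhere, and sets the calls one day later than Table 2

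*Protocol*

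**What the plan says.** **Scope.** Appendix 3 (A3-1) describes two calls, made "3 (± 1) days and 7 (± 1) days after the injection", to elicit reports of "adverse events that may have occurred (e.g., decrease in vision, eye pain, unusual redness, or any other new ocular symptoms) in the study eye". Section 8.3.1 is wider: "All adverse events (ocular and non-ocular) will be reported from the start of treatment until Day 7 after the faricimab PFS injection procedure". Section 9.3 plans descriptive summaries of both ocular and non-ocular events. Table 2 marks adverse events at both calls without naming an eye. Appendix 3 itself later describes the safety plan as "monitoring of safety events (including adverse events, serious adverse events, and adverse events of special interest) during the study period", again with no eye limit.

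**Timing.** The note to the schema in Section 1.2 fixes the numbering: "The injection procedure (study Day 1 in the schematic"). Table 2 lists the calls under Day 3 (±1) and Day 7 (±1). Appendix 3 counts the same numbers from the injection instead. Section 4.4 defines completion as "including the safety telephone call 7 days after administration of the PFS injection", and Section 1.2 adds: "Study end is 7 days after the injection in the last patient". Sections 8.3.1, A2-5.2 and A2-6 all end reporting on Day 7 after the injection. Section 8.3.1 then refers the reader to the schedule of activities: "until Day 7 after the faricimab PFS injection procedure (see Section 1.3"). Section 4.4 gives the reporting period after the last patient's injection a tolerance of ±1 day.

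**The concern.** The two calls are the only scheduled patient contacts after Day 1, so what they do not ask about is left largely to what patients volunteer. Sections 2.3 and 8.3.8 send sites to Appendix 3 for risk mitigation and event management, which makes it a plausible source for a call script. A site that followed its wording literally could ask less about the fellow eye and about non-ocular events. Both are in scope: Section 6.8.1 permits treatment of the fellow eye, and the events of special interest in Section 8.3.8 include potential drug-induced liver injury.

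On timing, a call at the edge of one window is on schedule under one passage and off schedule under another, although Section 8 treats adherence to the schedule as essential. The final day or two of reporting may also go unasked. The end date matters for reporting too. Inside the period all serious adverse events are reported. Afterwards, Section A2-6 asks only for serious events believed related to treatment. An unrelated serious event 7 days after injection (study Day 8) is therefore reportable on one reading of Day 7 and not on the other.

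**Working it through.** **Scope.** No arithmetic applies, so the passages are set side by side.

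- Appendix 3: any adverse event, ocular examples only, then the study-eye phrase. That phrase stands outside the parenthesis, so it limits the events elicited and not just the examples.
- Section 8.3.1: all events, ocular and non-ocular.
- Section 9.3: both kinds are summarised.
- Table 2: events are collected at both calls with no eye limit.
- Section 8: an interval medical history at each follow-up. Section 8.3.2: open questions are preferred.

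Every passage except the first supports the wider scope.

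**Day count.** Inputs: injection = study Day 1 (Section 1.2); calls on study Days 3 and 7, each ±1 (Table 2); calls 3 and 7 days after injection, each ±1 (Appendix 3).

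Formula: days after injection = study day − 1.

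| Call | Table 2, days after injection (early / target / late) | Appendix 3, days after injection (early / target / late) | Shared days | Conflicting days |
|---|---|---|---|---|
| First | 1 / 2 / 3 | 2 / 3 / 4 | 2, 3 | 1, 4 |
| Last | 5 / 6 / 7 | 6 / 7 / 8 | 6, 7 | 5, 8 |

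The shift is 3 − 2 = 1 day for the first call and 7 − 6 = 1 day for the last. Section 4.4's figure of 7 days after injection for the last call agrees with Appendix 3's target. Table 2's target gives 6, so the stated 7 is not reproduced from Table 2. Each target still lies inside the other passage's window: 2 is in 2-4, 3 is in 1-3, 6 is in 6-8, and 7 is in 5-7.

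**Gap between the last call and the end of reporting.** Gap = max(0, end of period − day of call), in days after injection.

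| Reading of Day 7 | End of period | Table 2 gap (early / target / late) | Appendix 3 gap (early / target / late) |
|---|---|---|---|
| 7 days after injection | 7 | 2 / 1 / 0 | 1 / 0 / 0 |
| Study Day 7 | 7 − 1 = 6 | 1 / 0 / 0 | 0 / 0 / 0 |

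The ±1 day in Section 4.4 is not combined with these figures, because it is stated for the period after the last patient's injection and not as a per-patient end date. The number of events missed cannot be derived, since the protocol gives no event rate or detection rate.

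**The case against.** The best case against the point is that the operative rules are already clear. Section 8.3.1 and Table 2 require all events, Section 8 binds sites to the schedule and asks for an interval history, and Section 8.3.2 prefers open questions. Patients are told to raise any health concern with the investigator (Appendices 3 and 9). On this view the study-eye phrase is a loose clause in a narrative appendix, and harm needs a site to script from it and ignore the rest. Much of that stands. A reader might infer that fellow-eye and non-ocular events will not be collected; the documents do not support this. What remains is that one instruction for the calls disagrees with the others.

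On timing, a reader might infer that Table 2's on-target last call necessarily falls a day before reporting ends. That is not established. It holds if reporting runs to 7 days after injection, a reading that Section 4.4 supports. It fails if Day 7 is the study day of the schedule to which Section 8.3.1 refers. The tolerance in Section 4.4 also shows that the boundary is not treated as sharp. The one-day shift between Table 2 and Appendix 3 stands on either reading.

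It is also fair to say that Section 3 plans no patient-related safety endpoint, that eye symptoms are to be reported at any time, including after the period, and that related serious events learned of later are still notified. What could go unasked is therefore mainly non-serious or non-ocular events.

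**Conclusion.** The point holds as a pair of minor internal contradictions. First, the study-eye phrase in Appendix 3 conflicts with the all-event scope of Sections 8.3.1 and 9.3 and Table 2. Second, Table 2 and Appendix 3 set both calls one day apart, with conflict only for a first call 1 or 4 days after injection or a last call 5 or 8 days after. A gap before the end of reporting is conditional. Under Table 2 it is 1 day on target and at most 2 if reporting ends 7 days after injection, and 0 on target and at most 1 if it ends on study Day 7.

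The result rests on injection being study Day 1, as Section 1.2 states. The consequence is possible incompleteness of descriptive safety data in about 35 patients. Section 9.1 plans no hypothesis test, so no inference is affected. The passages are still worth correcting, because they give conflicting instructions for the only scheduled contacts after Day 1.

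**What to change.** 1. In Appendix 3, remove the study-eye phrase as a limit. Have each call ask openly about any adverse event, in either eye or elsewhere in the body, and then about the listed ocular symptoms.
2. Reconcile Table 2, Sections 4.4 and 8.3.1, A2-5.2, A2-6 and Appendix 3 to one day count, either study day or days after injection, and check the schema note in Section 1.2 against it. If days after injection are kept, Table 2's calls become study Days 4 (±1) and 8 (±1). If study days are kept, the other passages change to match.
3. State the call window and the end of reporting together so that the last call does not precede the end. A single count alone closes the on-target gap, but it leaves 1 day at the early edge when the target equals the end date and the window is ±1. Either the window opens at the end of the period or the period is defined to close at the call.

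The cost is mostly wording, with no added visits or calls. The third step slightly changes the call window or the reporting period, and some last calls may fall a day or two later.
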